In addition, this study aims to explore a novel mechanism that may account for individual variability in the respiratory response to anesthesia. Short chain fatty acids are produced by the gut microbiome (non-pathological bacteria in the gastrointestinal tract). Low levels of these compounds have been associated with hypertension and obesity, as well as hypertension in people with sleep apnea. Receptors that are activated by these compounds are found in high concentration in the carotid body, where their activation appears to stimulate respiration. We will measure serum levels of short chain fatty acids, and hypothesize that lower concentrations will be associated with greater anesthesia induced respiratory depression and higher levels will be protective. If short chain fatty acids are shown to be associated with a protective affect on respiratory depression, this could open the door to an entirely new understanding of the mechanisms that contribute to respiratory depression during anesthesia, but also those involved with obstructive sleep apnea. In addition, it could raise the possibility that short chain fatty acids could be administered as a protective treatment.

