## **2. Objectives (include all primary and secondary objectives)**

Specific Aim 1: To test whether nasal CPAP reduces the incidence of hypoxia during procedural sedation with propofol as compared to usual care. Hypothesis: A randomized clinical trial of an intervention to reduce airway obstruction (nasal CPAP) will decrease the incidence of hypoxic events ( $<90\% \geq 15s$ ) compared to usual care in patients undergoing procedural sedation.

Specific Aim 2: To determine the duration, magnitude and mechanism of hypoventilation and its association with hypoxia in subjects undergoing procedural sedation. Hypothesis: By determining minute ventilation, transcutaneous CO2 and sedation depth while measuring end-tidal CO2, it will be possible to relate ventilation to hypoxic events, sedation depth and airway obstruction. Further, reductions in the incidence of hypoxia in the intervention group will be consistent with the hypothesis that loss of airway motor tone underlies hypoventilation and associated hypoxia.

Specific Aim 3: To characterize the physiologic state when end-tidal capnography is insufficient for detecting hypoventilation. Hypothesis: The amplitude of the capnographic signal is not representative of the adequacy of ventilation due to artifact from loss of airway motor tone during procedural sedation.

Specific Aim 4: To determine if there short chain fatty acid serum concentration is protective for procedural sedation induced hypoventilation, obstruction and hypoxia: Hypothesis: Higher concentration

of short chain fatty acids will be reduce the risk of hypoventilation, obstruction, and hypoxia and suggests a link between respiratory function and gut microbiome.

**3. Background** (briefly describe pre-clinical and clinical data, current experience with procedures, drug or device, and any other relevant information to justify the research)

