The large and growing number of GE procedures with anesthesia services underlies the importance of delivering safe care, as even a low rate of sedation related adverse events may affect a large number of patients. In several retrospective studies, cardiopulmonary events occurred in up to 11.7/1000 events, and hypoxia was the most common. While the full implication of mild transient hypoxia on outcomes is unknown, significant hypoventilation with hypercarbia and hypoxia commonly proceeds cardiopulmonary arrest. Respiratory depression from oversedation is an important mechanism of patient injury during monitored anesthesia care. The rate of hypoxia is considered as a marker for unsafe sedation practices in endoscopy suites. However, the true rate of hypoxia associated with sedation for endoscopic procedures is unknown and ranges from 1% to 70% in the literature. The variability may be related to adequacy of surveillance as well as differences in the definition of hypoxia. For instance, lower rates of hypoxia in manually and electronically recorded pulse oximetry data during clinical care have been reported. A recent study from the Netherlands reported a hypoxia rate in average risk patients during sedation for colonoscopy without oxygen supplementation of 55.6%. A recent study from Germany pseudorandomized patients undergoing upper, lower, or combined endoscopic procedures with propofolbased anesthesia to nasal cannula alone or with a nasopharyngeal airway and found rates of

hypoxia of 1.8% versus 13.5%. In another study from the Cleveland Clinic evaluating the STOP-BANG sleep apnea scoring system, subjects with STOP-BANG score >3 had a rate of hypoxia of 16.9% versus 11.2% in the STOP-BANG score <3 group, but this did not reach significance in this underpowered study. However, higher BMI was associated with more sedation-related adverse events (SRAE).

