Hypoxia is related to both centrally mediated changes in respiratory drive caused by sedative drugs, direct effects of the anesthetic agents on motor function, and diminished airway tone due to sleep or sedation (change in state). Furthermore, sedative agents decrease airway tone and increase the risk of obstruction, while blunting the normal arousal that occurs in response to hypercarbia and hypoxia during obstruction events during natural sleep. Obstructive sleep apnea and obesity are risk factors for airway obstruction during sedation. Use of nasal CPAP has been demonstrated to improve ventilation, alleviate upper airway obstruction, and reverse hypoxia in women undergoing spinal anesthesia with sedation for gynecological procedures. Continuous positive pressure stents the airway, alleviating the obstruction from oropharyngeal soft tissue that occurs during sleep and under sedation, and has been advocated in patients with obstructive sleep apnea on CPAP at home. Positive pressure ventilation using a nasal mask has also been shown to be effective. The Supernova mask (RMD medical, Tucson, AZ) is FDA approved commercially available nasal mask that can be attached to a standard anesthesia circuit or Jackson Reese, and allows for up to 30 l/min of oxygen delivery, making it convenient for use in procedural sedation. It can supply CPAP as well as supplemental positive pressure breaths by closing the mouth or applying gentle cephalad directed submandibular pressure to push close the oropharynx by approximation of the tongue and palate.

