Impedance based respiratory volume monitoring has been used to assess adequacy of ventilation and airway obstruction in patients undergoing endoscopic gastrointestinal procedures. In fact, such studies also suggest that EtCO2 often decreases as minute ventilation decreases. In this study, changes in minute ventilation from baseline, and episodes of upper airway obstruction will be assessed using the commercially available ExSpiron™ (Exspiron, Respiratory Motion Inc, Waltham MA). Previous studies using the ExSpiron™ have suggested that decreased minute ventilation during sedation for GE procedures is primarily due to decreased tidal volume rather than respiratory rate. Transcutaneous carbon dioxide has proven to closely approximate to arterial carbon dioxide (PaCO2), and in fact more closely reflects PaCO2 than end tidal carbon dioxide (EtCO2). Transcutaneous carbon dioxide (TcCO2) has been shown to closely correlate with PaCO2. After approximately 5 minutes of calibration time, it appears to track changes in PaCO2 with a lag time of 30 seconds to 2 minutes. In our experience using the TcCO2 monitor

for clinical application during jet ventilation, we have found the device to consistently track within 5 points of the PaCO2. (Sentec, Therwil, Switzerland).

Depth of anesthesia using processed electroencephalography has been described as a marker for depth of anesthesia during GETA and MAC with sedation. Depth of anesthesia using bispectral index (BIS) has been relatively well established and is known to correlate well with other measures of depth of anesthesia. We will use bispectral index (BIS) (Medtronic, Minneapolis, Minnesota) as a marker of state. In addition, all clinical data utilized in routine practice will be recorded, including drug dosing, method of drug administration, and length of stay in the recovery area.

Recently, alterations in the gut microbiome have been implicated in obesity, hypertension, obstructive sleep apnea induced hypertension, and airway smooth muscle tone that may relate to reactive airway disease. In general, lower short chain fatty acid levels are associated with pathology, and higher levels appear to be

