protective. Olfactory receptors located in vascular endothelium are activated by short chain fatty acids, causing smooth muscle relaxation, vasodilation, and protection from hypertension, with some feedback mechanisms that may prevent significant hypotension as well. Interestingly, these receptors are also highly expressed in the carotid body, where activation by short chain fatty acids increases respiratory drive. This is an intriguing possible mechanism for individual variability in susceptibility to anesthesia induced hypoventilation and may also be a contributing mechanism for hypoventilation in patients with sleep apnea. We hypothesize that lower serum concentration of short chain fatty acids will be associated with more respiratory depression and higher levels will be protective. Further, we suspect that patients with known obstructive sleep apnea, hypertension, and high BMI will have lower short chain fatty acid levels.

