#### **4. Study Procedures**

Study design, including the sequence and timing of study procedures (distinguish research procedures from those that are part of routine care).

This study is a randomized controlled trial comparing oxygen delivery with nasal CPAP versus standard care (delivery via nasal cannula or standard facemask) during propofol-based sedation for endoscopic procedures. The primary outcome will be the rate of oxygen desaturation below 90% for  $\geq 15$  seconds. Secondary outcomes are the degree of hypoventilation measured by continuous transcutaneous carbon dioxide (TcCO2), the change in minute ventilation (MV) and obstructive episodes measured by impedance-based respiratory volume monitoring, and depth of anesthesia measured by bispectral index (BIS) monitoring. The adequacy of standard ETCO2 monitoring will also be assessed. In addition, all clinical data utilized in routine practice will be recorded, including drug dosing, method of drug administration, blood pressure changes, frequency of interruption of procedure for airway maneuvers or rescue, length of stay in the recovery area, and any complications that are identified.

Subjects will be recruited from the patient population scheduled for MAC with sedation for gastrointestinal endoscopic procedures at the Johns Hopkins Hospital Endoscopy Center on Zayed 2. Patients scheduled for colonoscopy, EGD (including EGD with biopsy, ultrasound, PEG

placement, or enteroscopy ) or combined upper and lower endoscopic procedures predicted to last longer than 10 minutes and for which MAC with sedation is the planned anesthetic technique will

Page 5 of 12

be considered for the study. A study team member will screen the endoscopy schedule for potential subjects. We will direct our recruitment to patients with documented OSA or a BMI  $\geq 30$ , but we not limit it to just those patients. Written, informed consent will be obtained from interested eligible subjects or their representative.

As part of routine care, all patients undergoing MAC with sedation receive an IV in the preoperative area. During the placement of this IV up to 15 mL of blood will be collected for short chain fatty acids measurements and possibly the measurement of biomarkers and other compounds. The written consent form will include permission from the participant to store their blood for future research.

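### Does Aim 4 need a prespecified, covariate-adjusted model for serum short chain fatty acids?

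*Combined protocol and SAP*

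**What the plan says.** Section 2 (Specific Aim 4) asks whether "short chain fatty acid serum concentration is protective for procedural sedation induced hypoventilation, obstruction and hypoxia". Its hypothesis ends more softly, speaking only of a suggested link between respiratory function and the gut microbiome. The Abstract describes the SCFA work as exploring a new mechanism, then adds that, given a positive result, "short chain fatty acids could be administered as a protective treatment". Section 3 calls SCFA a predictor and possible mechanism.

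SCFA is measured in blood drawn when the routine IV is placed (Section 4). Only nasal CPAP versus standard oxygen is randomised.

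On the link between patient factors and SCFA, the Abstract reports low levels with obesity and hypertension, and Section 3 adds: "we suspect that patients with known obstructive sleep apnea, hypertension, and high BMI will have lower short chain fatty acid levels".

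On the link between patient factors and outcomes, Section 3 states: "Obstructive sleep apnea and obesity are risk factors for airway obstruction during sedation". It also reports that "higher BMI was associated with more sedation-related adverse events". In a cited cohort, patients with a higher sleep-apnoea score "had a rate of hypoxia of 16.9% versus 11.2% in the STOP-BANG score <3 group", a difference that was not significant.

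Section 7 mentions SCFA once, as a batched analysis after the first 20 subjects. Otherwise it gives general methods: Fisher's exact test for frequencies, regression or an equivalent for continuous data, mixed models for longitudinal data, and a logistic regression relating demographic information to hypoxic events. None names SCFA as a predictor, and no covariates are listed. SCFA is not among the secondary outcomes in Section 4 or Section 7.

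**The concern.** The aim uses causal language about an exposure that nobody assigned. The protocol itself supplies reasons to expect confounding: heavier patients and those with obstructive sleep apnoea (OSA) may have lower SCFA, and they obstruct more under sedation. A regression of outcome on SCFA alone could then show a protective association with no SCFA effect behind it. These factors will vary in the sample, because Section 4 says "We will direct our recruitment to patients with documented OSA or a BMI" of 30 or more without restricting entry to such patients.

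There is a second difficulty. Section 3 also says that "alterations in the gut microbiome have been implicated in obesity, hypertension" and other conditions, and that the SCFA mechanism may contribute to hypoventilation in sleep apnoea. On that reading BMI or OSA may lie on the causal path, and adjusting for them would remove part of a real effect. The plan does not say which reading it adopts. If the model were chosen after the 20-subject batch, the choice might follow the data. At stake would be a false lead towards SCFA as a treatment.

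**Working it through.** **The plan's own figure.** Section 7 gives no number for Aim 4, but its sample size fixes n. With 13.5% versus 1.8%, two-sided alpha 0.05 and power 0.90, the pooled formula is

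n = [1.960·√(2·0.0765·0.9235) + 1.282·√(0.135·0.865 + 0.018·0.982)]² / 0.117² = (0.737 + 0.470)² / 0.01369 ≈ 107 per arm.

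The stated 109 is reproduced closely; exact Fisher power at 109 per arm is 0.908. So n = 218 completers. Expected hypoxia events are 109 × (0.135 + 0.018) = 16.7, or 120 × 0.153 = 18.4 if all 240 enrolled contribute.

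**Continuous outcome, no true SCFA effect.** Let a be the confounder–SCFA correlation and b the confounder–outcome correlation. Both are assumed; the documents give neither. The spurious correlation is a·b, and the rejection rate is approximately P(|Z + atanh(ab)·√(n−3)| > 1.96). For a = b = 0.3: atanh(0.09)·√215 = 1.323, and Φ(1.323 − 1.96) plus a negligible lower tail is 26%.

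| a, b | Unadjusted false positives (n = 218) |
|---|---|
| 0.1, 0.1 | 5% |
| 0.3, 0.1 | 7% |
| 0.2, 0.2 | 9% |
| 0.3, 0.2 | 14% |
| 0.4, 0.2 | 22% |
| 0.3, 0.3 | 26% |
| 0.4, 0.4 | 66% |

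A separate simulation used a binary factor of 50% prevalence that shifts both SCFA and the outcome by 0.3 to 0.8 SD. It gave about 7% to 53% unadjusted and 4% to 6% after adjustment. Everything from negligible to serious is available, depending on what is assumed.

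**Hypoxia, using the one documented contrast.** Odds ratio = (0.169/0.831) / (0.112/0.888) = 1.61. It was entered as a binary confounder at an assumed 50% prevalence, with the design event rates, 109 per arm and 3000 replicates:

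| SCFA correlation (assumed) | Unadjusted | Adjusted for arm and confounder |
|---|---|---|
| 0.2 | 5.6% | 5.8% |
| 0.3 | 6.0% | 4.7% |
| 0.4 | 6.9% | 4.8% |

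Monte Carlo error near 5% is √(0.05·0.95/3000) = 0.4 points. At 0.2 there is no visible difference, and at 0.4 the excess is under two points. A stronger assumed confounder (odds ratio 2 per SD) gives 7%, 11% and 16%.

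**Cost of adjusting.** The ratio of adjusted to unadjusted standard errors is √[(1−b²)/((1−a²)(1−a²b²))]·√[(n−2)/(n−4)]. It is 1.09 at a = 0.4, b = 0.1; 1.01 at 0.3, 0.3; and 0.93 at 0.1, 0.4. Precision does not decide the matter.

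**What the 20-subject batch could reveal.** Expected hypoxia events are 20 × 0.0765 = 1.5 with equal arms. For a continuous outcome, the 95% limits around a zero correlation are ±tanh(1.96/√17) = ±0.44. Data this thin are a poor guide for choosing a model to suit the result. Section 7 pairs the batch with a check of complete data collection, so it can also be read as a laboratory or feasibility step.

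**How firm the links are.** Obesity and hypertension with low SCFA: reported. OSA with low SCFA: only suspected. OSA and obesity with obstruction: stated. BMI with sedation-related adverse events: stated, though not specifically respiratory ones. BMI or OSA with hypoventilation under anaesthesia, the first Aim 4 outcome: not stated. The case for confounding is clearest for obstruction, for which the documents give no rate.

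**The case for a change.** The best case for a change runs as follows. Aim 4 is one of four numbered aims and uses the language of protection. The protocol contains both halves of a confounding path and also hints at a mediating path. Adjusted and unadjusted estimates may disagree, and nothing fixes in advance which one carries the conclusion. A few lines in Section 7 would settle it, with no new data: BMI and documented OSA already direct recruitment, and Section 4 links demographic and clinical data to the physiological record.

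Much of this stands. There is no SCFA-specific model, the wording of the aim is stronger than the design supports, and a reader should not take an unadjusted SCFA association as evidence of protection.

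What does not follow is that the plan is wrong. Unnamed covariates in a secondary, partly exploratory analysis are a gap that an analyst fills as a matter of course; the regression named in Section 7 accommodates BMI, OSA and arm. Naming covariates would not resolve the confounder-or-mediator question either, because the protocol's own biology supports both readings. Nor would a covariate list complete the specification: the SCFA scale, the per-patient summaries of hypoventilation and obstruction, and the place of hypertension would still be open. For hypoxia, some 17 events leave room for very few covariates under any plan.

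**Conclusion.** The gap is real but minor, and no change to the plan is needed. Section 7 leaves the SCFA model open; it does not plan an unadjusted test. The harm arises only if analysts ignore covariates that they hold and that the protocol itself discusses.

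For hypoxia, the documented contrast puts the unadjusted false-positive rate at about 6% to 7% instead of 5%, assuming 50% prevalence and an SCFA correlation of 0.2 to 0.4. For continuous respiratory outcomes the rate could lie anywhere from 5% to 66% across the correlations tried, and the documents give nothing with which to narrow that range, so the upper figures should carry no weight. Whether to adjust for BMI and OSA is a fair trade-off between confounding and over-adjustment. Any SCFA finding here is naturally read as an association, which is how much of the Abstract and Section 3 already frames it. The randomised comparison of hypoxia between arms does not depend on any of this.

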#### **4. Study Procedures**

Study design, including the sequence and timing of study procedures (distinguish research procedures from those that are part of routine care).

This study is a randomized controlled trial comparing oxygen delivery with nasal CPAP versus standard care (delivery via nasal cannula or standard facemask) during propofol-based sedation for endoscopic procedures. The primary outcome will be the rate of oxygen desaturation below 90% for  $\geq 15$  seconds. Secondary outcomes are the degree of hypoventilation measured by continuous transcutaneous carbon dioxide (TcCO2), the change in minute ventilation (MV) and obstructive episodes measured by impedance-based respiratory volume monitoring, and depth of anesthesia measured by bispectral index (BIS) monitoring. The adequacy of standard ETCO2 monitoring will also be assessed. In addition, all clinical data utilized in routine practice will be recorded, including drug dosing, method of drug administration, blood pressure changes, frequency of interruption of procedure for airway maneuvers or rescue, length of stay in the recovery area, and any complications that are identified.

Subjects will be recruited from the patient population scheduled for MAC with sedation for gastrointestinal endoscopic procedures at the Johns Hopkins Hospital Endoscopy Center on Zayed 2. Patients scheduled for colonoscopy, EGD (including EGD with biopsy, ultrasound, PEG

placement, or enteroscopy ) or combined upper and lower endoscopic procedures predicted to last longer than 10 minutes and for which MAC with sedation is the planned anesthetic technique will

Page 5 of 12

be considered for the study. A study team member will screen the endoscopy schedule for potential subjects. We will direct our recruitment to patients with documented OSA or a BMI  $\geq 30$ , but we not limit it to just those patients. Written, informed consent will be obtained from interested eligible subjects or their representative.

As part of routine care, all patients undergoing MAC with sedation receive an IV in the preoperative area. During the placement of this IV up to 15 mL of blood will be collected for short chain fatty acids measurements and possibly the measurement of biomarkers and other compounds. The written consent form will include permission from the participant to store their blood for future research.

All subjects enrolled in the study will have research monitors placed on the skin in a similar fashion to the pads for ekg lead placement, with respiratory volume monitoring on the chest, BIS and TcCO2 on the forehead. All enrolled subjects will be connected to the ExSpirom™ monitor (Respiratory Motion, Inc., Waltham MA) and digital respiratory traces of MV, TV, and RR measurements will be collected on all 240 patients. The ExSpirom monitor uses an adhesive, latexfree, adjustable 5 sensor strip applied to the chest to measure the amount of air moving in and out of the lung in real time. Minute ventilation will also be correlated to transcutaneous CO2 as measured by the SenTec Digital Monitor (SenTec AG, Therwil, Switzerland). Transcutaneous CO2 (Ptc CO2) monitoring provides a noninvasive technique allowing continuous monitoring of ventilation. It is based on arterialization of the capillary bed through the local application of heat and the use of Stow-Severinghaus electrodes. The sensor will be calibrated, applied to the patient's forehead, cheek, or chest, and warmed to a constant surface temperature of 42 °C. In adults, these temperatures are safe for up to 24h, and the procedures performed in this study are generally less than 2 hours. The BIS monitor is also an adhesive strip with 4 sensors applied to the subjects forehead.

All subjects will also have standard, routine monitors placed by the treating team, including blood pressure, ECG, pulse oximetry, and EtCO2. Subjects will be randomized to either 1) receive oxygen by nasal mask (nCPAP) with CPAP of 10 mmHg or 2) standard oxygen therapy. Subjects randomized to nCPAP will have a nasal facemask (SuperNOVA) placed approximately 5 minutes prior to the procedural start. The mask attaches to the anesthesia circuit, oxygen flow will be set at 10 lpm, and the CPAP of 10 will be set by turning the "pop-off" valve to 10 mmHg. Subjects randomized to standard care will have oxygen delivered by nasal cannula or simple facemask with oxygen level set by the treating providers. The CPAP level of 10 will be chosen because previous studies suggest that 95% of airway obstruction can be alleviated with a CPAP of 7.1, and it is convenient marked on the anesthesia "pop-off" valve, ensuring standardization. For the CPAP group, flow below 10 lpm will be allowed in cases in which the patient or provider does not tolerate higher flows. For practicality, providers and patients will not be blinded to the intervention because application of the nasal mask is obvious. While the clinical team will have access to all of the routine monitors, they will be blinded to the research monitor data, which will include TcCO2 monitoring, respiratory volume monitoring (RVM), and BIS. Researchers analyzing the data will be blinded to the intervention.

All subjects will receive a routine propofol-based anesthetic per the treating clinical team. A study team member will record all airway maneuvers or interventions performed by the anesthesia team during the procedure, including changes in oxygen flow, ventilatory assistance, jaw thrust, or placement of an oral or nasal airway. Further, the duration of the endoscopic procedure and any anesthesia related interruptions will be recorded. The study duration will be entirely within the time period of the patients' visit to the endoscopy suite. All study monitors will be removed when the participants are discharged to home or transferred to the ward depending on the clinical routine or needs.

Each subject will be assigned a study number to allow connection of the demographic data and clinical characteristics for comparison with the physiological data. All analog data for vital signs will be digitized using a digital to analog converter and processed using commercially available software. Medication data and length of stay data will be collected directly from EPIC .

Additionally, data relating to any respiratory events (decreased RR, oxygen saturation, airway obstruction, etc.) requiring intervention will be recorded. Raw data from the ExSpiron™ monitor, actigraph device, and transcutaneous monitor will be stored in a separate file with the file name being the study number assigned above. There will be no patient identifiers in these files.

a. Study duration and number of study visits required of research participants.

Enrollment and data collection will begin after IRB approval. For each subject, the study will be performed entirely within their visit to the endoscopy suite. No additional visits will be required of study participants.

b. Blinding, including justification for blinding or not blinding the trial, if applicable.

The clinical team will have access to all of the routine monitors, but they will be blinded to the research monitor data, which will include TcCO2 monitoring, respiratory volume monitoring (RVM), and BIS. For practicality, providers and patients will not be blinded to the intervention because application of the nasal mask is obvious. Researchers analyzing the data will be blinded to the intervention.

c. Justification of why participants will not receive routine care or will have current therapy stopped.

Except for the application of study monitors to the skin and nasal CPAP in the treatment group, all subjects will receive routine anesthesia care to facilitate the planned procedure. The procedure will not be effected by participation in the study.

d. Justification for inclusion of a placebo or non-treatment group. Not applicable

e. Definition of treatment failure or participant removal criteria.

If a case is aborted because of procedural problems and no anesthesia was provided or the duration of the procedure was too short to obtain data, the participant would meet criteria for removal from the study. However, if an anesthetic requires change to an alternate anesthesia plan (such as conversion to general anesthesia) this will be recorded in the analysis.

f. Description of what happens to participants receiving therapy when study ends or if a participant's participation in the study ends prematurely.

If a participant's participation ends prematurely, they will receive routine care.

